6.14. Pharmacokinetic/Pharmacodynamic Methods

Details of the pharmacokinetic/pharmacodynamic (PK/PD) analyses can be found in a separate PK/PD analysis plan and are summarized briefly below.

Observed ixekizumab serum concentrations will be summarized by visits and corresponding time when sampling occurred.

As appropriate, the PK and the exposure-response relationship between ixekizumab exposure and clinically important efficacy measures (for example, sPGA or mGPASI) may be explored using graphical methods and/or a modeling approach. If a modeling approach is taken, data may be combined with data from other ixekizumab studies if appropriate.

The potential impact of immunogenicity on ixekizumab exposure and/or efficacy responses may be evaluated by graphical assessments, as appropriate, to compare drug exposure or efficacy responses between ADA negative and ADA positive patients at corresponding visits, or before and after ADA development for patients who developed ADA. Both treatment-emergent only and all ADA positive/negative patients may be explored. A similar approach may be taken if patients become neutralizing anti-drug antibody (NAb) positive.

Additional analyses may be performed upon receipt of the data. Data from this study may be combined with data from previous efficacy studies for additional population PK and/or exposure efficacy modelling if deemed appropriate.

6.15. Safety Analyses

Safety will be assessed by summarizing and analyzing AEs including adjudicated cerebro-cardiovascular events, QIDS-SR16, C-SSRS, laboratory analytes, and vital signs. The duration of exposure will also be summarized.

For the Blinded Treatment Period (Period 2), safety data will be summarized using the safety population. Treatment group comparisons between ixekizumab Q2W and placebo will be performed on categorical safety data using a Fisher's exact test and continuous safety data will be analyzed by an ANCOVA model with treatment group and baseline as factors.

For the Open-label Treatment Period (Period 3), safety data will be summarized according to the treatment group to which they were assigned in Period 2 and Period 3 (i.e. IXE80Q2W/IXE80Q4W and PBO/IXE80Q4W) and overall.

For the Post-Treatment Follow-up Period (Period 4), safety data will be summarized according to the treatment group in Period 2 or Period 3 (i.e. prior to entering Period 4) as described in [Table RHBQ.6.1](#).

For safety analyses, the following baselines will be used:

- Treatment-emergent adverse events (TEAEs): baseline will be all results recorded during the baseline period (see Section 6.1.2 for definitions of the baseline period).
- Change from baseline to last observation and each scheduled post-baseline visit for laboratory and vital signs: baseline will be last non-missing assessment recorded during the baseline period (see Section 6.1.2 for definitions of the baseline period).
- Treatment-emergent abnormal laboratory and vital signs: baseline will be all results recorded during the baseline period (see Section 6.1.2 for definitions of the baseline period).
- Change from baseline to minimum or maximum: baseline will be all results recorded during the baseline period (see Section 6.1.2 for definitions of the baseline period).

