4.4. Justification for Dose

The ixekizumab dosing regimen of ixekizumab 80 mg Q2W for 12 weeks (starting dose 160 mg) and ixekizumab 80 mg Q4W for 40 weeks was chosen based on results from the pivotal Phase 3 studies which provided safety and efficacy data for Q2W/Q4W dosing and Q4W/Q4W dosing following an initial dose of 160 mg. These studies did not evaluate Q2W dosing beyond 12 weeks; however, continuous Q2W dosing is being evaluated in an ongoing study, I1F-MC-RHBP.

As no treatment to date has been demonstrated to be effective and safe for the treatment of moderate-to-severe genital psoriasis in a controlled trial, placebo will be included as the comparator.

Study RHBQ is designed to assess the efficacy and safety profile of the Q2W regimen in the first 12 weeks (Blinded Treatment Period, Period 2) in patients with genital psoriasis. In addition, the study will collect long-term safety data for patients taking Q4W in the Open-Label Treatment Period (Period 3), as well as for those initially taking Q4W who increase dose frequency to Q2W of ixekizumab during the Open-Label Treatment Period (Period 3) if they do not achieve or maintain satisfactory disease control ([Section 6.1](#)).

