At Week 12, during the Open-Label Treatment Period (Period 3), all patients will be reassigned to ixekizumab 80 mg Q4W. Patients originally assigned to placebo will receive a blinded ixekizumab starting dose of 160 mg as 2 SC injections. To maintain blinding, patients originally assigned to ixekizumab 80 mg Q2W will receive a blinded ixekizumab 80-mg dose and a placebo dose at Week 12. Dosing may be increased in the Open-Label Treatment Period (Period 3) to ixekizumab 80 mg Q2W, starting at Week 24 through Week 40 (at Visit 9 [Week 24], Visit 10 [Week 28], or Visit 11 [Week 40]), if the patient is eligible to receive additional investigational product (that is, if it is determined by the patient and the investigator that the patient needs additional ixekizumab in order to achieve or maintain satisfactory disease control). All patients who increase dosing to 80 mg Q2W will remain on this dose until completion of the treatment period or early discontinuation. [Table RHBQ.6.1](#) shows the treatment regimens. If patients remain on ixekizumab 80 mg Q4W, their last dose will occur at Week 48. If patients step up to ixekizumab 80 mg Q2W, their last dose will occur at Week 50.

Treatment received during the Blinded Treatment Period (Period 2) will remain blinded to investigators, study site personnel, and patients until all patients have completed Week 52

(Visit 12) or have discontinued from the study (moved into Post-Treatment Follow-Up [Period 4]).

The investigator or his/her designee is responsible for the following:

- explaining the correct use of the investigational product to the patient/patient caregiver
- verifying that instructions are followed properly
- maintaining accurate records of investigational product dispensing, collection, and administration
- returning all unused medication to Lilly or its designee at the end of the study

Patients will be instructed to contact the investigator as soon as possible if he or she has a complaint or problem with the investigational product so that the situation can be assessed.

Further instructions and special considerations for the administration of the investigational product are provided in Sections [6.2.1](#) and [6.6.1](#).

Table RHBQ.6.1. Treatment Regimens

Randomized Treatment Arm	Dose Week 0 (Day 1)	Dose Week 2 to Week 10	Dose Week 12	Dose Week 16 to Week 50 ^a
	Blinded Dosing		Open-Label Dosing	

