6.1. General Considerations

Statistical analysis of this study will be the responsibility of Eli Lilly and Company (hereafter Lilly). The statistical analyses will be performed using SAS® Version 9.2 or higher.

Change from baseline at a particular visit will be calculated as the value at that visit minus the baseline value.

The means and medians will be reported to 1 more decimal place than the raw data recorded in the database. The standard deviation (SD) will be reported to 2 more decimal places than the raw data recorded in the database. In general, the maximum number of decimal places reported shall be 4 for any summary statistic.

Percentages will be presented to 1 decimal place. Percentages will not be presented for zero counts.

For outcome measures that are not collected at each post-baseline visit, data may exist at visits where the outcome measure was not scheduled to be collected, due to ETVs. In these situations, data from the ETVs that do not correspond to the planned collection schedule will be excluded from any mixed-effects models for repeated measures (MMRM) analysis. However, the data will still be used in other analyses, including shift analyses and other categorical analyses.

General Considerations for Analyses during Blinded Treatment Period (Period 2)

Comparisons of ixekizumab Q2W dosing versus placebo will be performed for all outcome variables in Period 2.

All confidence intervals (CIs) and statistical tests will be 2-sided unless otherwise specified. p-values which are greater than or equal to 0.001, and less than or equal to 0.999, will be presented to three decimal places. All other p-values which are less than 0.001 will be presented as <0.001, while p-values greater than 0.999 will be presented as >0.999. Confidence intervals will be presented to one more decimal place than the raw data.

General Considerations for Analyses during Open-label Treatment Period (Period 3)

Only summary statistics will be presented for the treatment groups:

- Ixekizumab 80 mg, every 2 weeks/every 4 weeks (IXE80Q2W/IXE80Q4W): Patients who received ixekizumab Q2W in the Blinded Treatment Period and ixekizumab Q4W in the Open-label Treatment Period (including those who stepped up to ixekizumab Q2W).
- Placebo/ixekizumab 80 mg, every 4 weeks (PBO/IXE80Q4W): Patients who received placebo in the Blinded Treatment Period and ixekizumab Q4W in the Open-label Treatment Period (including those who stepped up to ixekizumab Q2W).

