- Overall: Unless otherwise specified, no comparisons between IXE80Q2W/IXE80Q4W and PBO/IXE80Q4W will be performed for any outcome variable in Period 3.

Data from patients who step up to ixekizumab Q2W dosing will be included in the efficacy summaries using the Open-label Treatment Population and the treatment groups defined above. The tables, figures, and listings will include footnotes indicating that patients were allowed to increase to Q2W dosing during the Open-label Treatment Period.

The number of patients who step up to Q2W dosing in Period 3 will be summarized by visit and overall using the treatment groups defined above. Patients who step up to Q2W dosing will be flagged in some efficacy and safety listings as deemed appropriate. A separate efficacy listing of sPGA of Genitalia and modified Genital Psoriasis Area and Severity Index (mGPASI) will be provided for patients who step up to Q2W dosing indicating the visits at which the patients started Q2W dosing.

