6.15.1. Extent of Exposure

Duration of exposure to study drug during the Blinded Treatment Period (Period 2) will be summarized by treatment group for the safety population using descriptive statistics. Duration of exposure in the Open-label Treatment Period (Period 3) will be summarized by ixekizumab Q4W only and ixekizumab Q4W step up to Q2W groups and overall using the Open-label Treatment Population.

A by-patient listing of exposure duration with number of active injections and total dose will be provided.

Duration of Exposure to Study Treatment during the Blinded Treatment Period (Period 2)

The duration of exposure to ixekizumab Q2W in Period 2 will be calculated as:

Duration of exposure to Q2W (days)

= *Date of last visit (scheduled or unscheduled) in Period 2 – Date of first dose + 1*

The number and percentage of patients in each of the following categories will be included in the summaries:

- >0, ≥7 days, ≥14 days, ≥30 days, ≥60 days, ≥90 days. Note that the same patients may be included in more than 1 category.
- >0 to <7 days, ≥7 to <14 days, ≥14 to <30 days, ≥30 to <60 days, ≥60 days to <90 days and ≥90 days

The summaries will also include the following information:

- Total exposure in patient years, calculated as:

Exposure in patient years

=
$$\frac{\text{Sum of duration of exposure for Period 2 (for all patients in treatment group)}}{365.25}$$

- Number of active injections taken: this is derived using the response to the question “Was dose administered?” on the Exposure eCRF page and the actual dose description from IWRS study drug dispense dataset
- Total dose (in mg): this is calculated by the number of active injections taken during Period 2 multiplies by a dose of 80 mg

Duration of Exposure to Study Treatment during the Open-Label Treatment Period (Period 3)

The duration of exposure to ixekizumab Q4W only or ixekizumab Q4W step up to Q2W dosing in Period 3 will be calculated as:

Duration of exposure (days)

= *Date of last visit (scheduled or unscheduled) in Period 3]*

– *Date of first Q4W dosing in Period 3 + 1*

The number and percentage of patients in each of the following categories will be included in the summaries:

- >0, ≥7 days, ≥14 days, ≥30 days, ≥60 days, ≥90 days, ≥120 days, ≥180 days, and ≥280 days. Note that the same patients may be included in more than 1 category.

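### The SAP splits Period 3 exposure by step-up status but no Period 3 event or efficacy summary, so no planned table gives event rates for the two groups protocol 4.4 names

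*SAP*

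**What the plan says.** **Purpose.** Protocol 4.4 says the study will collect long-term safety data for patients on Q4W in Period 3, "as well as for those initially taking Q4W who increase dose frequency to Q2W of ixekizumab" in that period. Under protocol 6.1, step-up at Week 24, 28 or 40 is open when patient and investigator agree that "the patient needs additional ixekizumab in order to achieve or maintain satisfactory disease control".

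**Safety grouping.** For Period 3, SAP 6.15 says "safety data will be summarized according to the treatment group to which they were assigned in Period 2 and Period 3", meaning IXE80Q2W/IXE80Q4W and PBO/IXE80Q4W, plus an overall column. SAP 6.1 defines each group as patients who received "ixekizumab Q4W in the Open-label Treatment Period (including those who stepped up to ixekizumab Q2W"). SAP 6.15.2, 6.15.2.1, 6.15.3.1 and 6.15.4 add no division by step-up status for TEAEs, common TEAEs, special safety topics or laboratory tests.

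**Exposure.** SAP 6.15.1 does divide: Period 3 duration "will be summarized by ixekizumab Q4W only and ixekizumab Q4W step up to Q2W groups" and overall. Duration runs from the first Q4W dose in Period 3 to the last Period 3 visit.

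**Efficacy.** SAP 6.1: "Data from patients who step up to ixekizumab Q2W dosing will be included in the efficacy summaries", under the same two groups.

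**Where step-up is visible.** SAP 6.1 plans counts of step-ups by visit and overall, footnotes on displays, flags in some listings, and a separate listing of sPGA of Genitalia and mGPASI showing the visit at which Q2W began. SAP Table RHBQ.6.1 has separate IXE80Q2W and IXE80Q4W rows for Period 4.

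**The concern.** The protocol names two groups for long-term safety, and the SAP recognises the same two when it tabulates exposure. The event tables then merge them. A reader of the study report would have exposure columns without matching event counts, and event columns in which patients on different dosing frequencies share one Q4W label.

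Two things are at stake. An event that was more frequent after step-up would be averaged into the larger group and would not appear in any planned summary. And a Week 52 response shown under a Q4W label would include responses seen after the patient had left Q4W, with only a footnote to say that step-up was allowed.

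**Working it through.** **1. The plan's own dosing figures reproduce.** SAP 6.9 gives 11 Period 3 injections for Q4W throughout: 2 at Week 12 plus 9 at Weeks 16 to 48. For step-up at week x it gives 2 + (x − 12)/4 + (50 − x)/2:

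- x = 24: 2 + 3 + 13 = 18
- x = 28: 2 + 4 + 11 = 17
- x = 40: 2 + 7 + 5 = 14

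A direct count of scheduled doses agrees each time. From Week 24 on, a patient who steps up at Week 24 is scheduled 14 doses (every 2 weeks, Weeks 24 to 50) against 7 on Q4W (Weeks 24 to 48). Scheduled dose can therefore differ two-fold under one label.

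**2. What the step-up exposure column contains.** Period 3 runs from Week 12 to Week 52, or 40 weeks. For a patient who completes it, Q4W time before step-up is x − 12 weeks and Q2W time is 52 − x weeks.

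| Step-up week | Q4W weeks | Q4W share | Q2W weeks | Q2W share |
|---|---|---|---|---|
| 24 | 12 | 12/40 = 30% | 28 | 70% |
| 28 | 16 | 16/40 = 40% | 24 | 60% |
| 40 | 28 | 28/40 = 70% | 12 | 30% |

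Dividing post-step-up events by this exposure would give 0.7, 0.6 or 0.3 of the rate per unit of actual Q2W time. In addition, SAP 6.15.1 specifies total patient-years for Period 2 but not for Period 3.

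**3. Dilution of an event signal (assumed inputs).** The documents give no step-up rate. Let a share s of patients step up, and suppose an event has 5% incidence without step-up and 15% with it. The pooled figure is 15s + 5(1 − s) per cent: 5.5% at s = 5%, 6% at s = 10%, 7% at s = 20% and 8% at s = 30%. If all 146 randomised patients entered Period 3, these shares are about 7, 15, 29 and 44 patients.

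**4. Efficacy (assumed inputs).** If a share r of stepped-up patients respond at Week 52, the pooled response exceeds response reached without step-up by s × r. With r from 30% to 70%, that is 1.5 to 3.5 points at s = 5%, 3 to 7 at 10%, 6 to 14 at 20% and 9 to 21 at 30%.

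**The case against.** The strongest case on the other side has four parts.

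- **The data are there.** A reader might infer that the trial cannot describe safety by regimen. The documents do not support that. Step-up visits are recorded, all AEs are listed by patient (SAP 6.15.2), exposure listings carry active injections and total dose (SAP 6.15.1), and step-up counts are tabulated. What is missing is a planned summary.
- **The protocol does not promise separate tables.** Section 4.4 speaks of collecting data, and it points to another ongoing study for continuous Q2W dosing. This stands. It weakens any claim that long-term Q2W safety depends on this trial, but not the observation that both groups are named and only exposure is divided between them.
- **The pooled efficacy row is legitimate.** Protocol Table RHBQ.6.1 makes optional step-up part of the Period 3 regimen, protocol 9.3 requires analysis by Period 2 assignment, and the SAP states the inclusion openly. A reader might infer that the pooled Week 52 response is biased upward. It is not. It answers a different question from response on Q4W alone. Step-up is also not triggered by an sPGA of Genitalia threshold, so a patient already at 0 or 1 could step up.
- **The exposure group is accurately named.** It describes the sequence of Q4W then Q2W and is not labelled Q2W exposure. This stands; the shares in the working matter only if the column is used as a denominator for Q2W events.

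The Period 4 rows help only in part. They cover follow-up, and the IXE80Q2W row could mix stepped-up patients with patients who stopped Q2W during Period 2.

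**Conclusion.** The point holds as a gap in the planned summaries. Period 3 exposure is divided by step-up status, while adverse events, special-interest events, laboratory results and efficacy are not. The plan therefore gives no event incidence or rate for either group named in protocol 4.4. The counts, footnotes, flags, separate listing and Period 4 rows mitigate this only partly.

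The firm figures are the 30%, 40% and 70% of step-up exposure spent on Q4W, which assume that the patient completes Week 52 and steps up on schedule. The dilution and response ranges rest on assumed step-up shares, event rates and response rates, so the true sizes are unknown. The response range is a distance between two estimands, not an error in the planned figure.

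Period 3 is descriptive with no planned comparison between groups, and the Week 12 primary and gated secondary tests are unaffected. This is an inexpensive improvement worth making, not a threat to the trial's conclusions.

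**What to change.** **Safety (SAP 6.15 and 6.15.1).** Add descriptive Period 3 summaries of TEAEs, SAEs and AESIs with events and person-time split at the step-up date: Q4W time, from all patients, up to step-up or the end of the period; and Q2W time after step-up. Give exposure-adjusted rates for each. Splitting at the date is better than grouping by eventual status, because a patient must still be on treatment at Week 24 or later to step up. State beside the tables that the split is not randomised and is confounded by calendar time and disease severity.

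**Efficacy (SAP 6.1), optional.** Keep the planned all-patients row, but label it as Q4W with optional Q2W step-up. Beside it, for sPGA of Genitalia (0,1) and overall sPGA (0,1), add a supportive row at post-step-up visits through Week 52 (Weeks 28, 40 and 52) that counts stepped-up patients as not responding on Q4W alone. Label it as a different estimand.

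**Cost.** SAP wording and a few tables from data already collected, with no change to dosing or conduct. The step-up column may be small and its rates imprecise, and the response figure for Q4W alone cannot be higher than the pooled one.

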6.15.1. Extent of Exposure

Duration of exposure to study drug during the Blinded Treatment Period (Period 2) will be summarized by treatment group for the safety population using descriptive statistics. Duration of exposure in the Open-label Treatment Period (Period 3) will be summarized by ixekizumab Q4W only and ixekizumab Q4W step up to Q2W groups and overall using the Open-label Treatment Population.

A by-patient listing of exposure duration with number of active injections and total dose will be provided.

Duration of Exposure to Study Treatment during the Blinded Treatment Period (Period 2)

The duration of exposure to ixekizumab Q2W in Period 2 will be calculated as:

Duration of exposure to Q2W (days)

= *Date of last visit (scheduled or unscheduled) in Period 2 – Date of first dose + 1*

The number and percentage of patients in each of the following categories will be included in the summaries:

- >0, ≥7 days, ≥14 days, ≥30 days, ≥60 days, ≥90 days. Note that the same patients may be included in more than 1 category.
- >0 to <7 days, ≥7 to <14 days, ≥14 to <30 days, ≥30 to <60 days, ≥60 days to <90 days and ≥90 days

The summaries will also include the following information:

- Total exposure in patient years, calculated as:

Exposure in patient years

=
$$\frac{\text{Sum of duration of exposure for Period 2 (for all patients in treatment group)}}{365.25}$$

- Number of active injections taken: this is derived using the response to the question “Was dose administered?” on the Exposure eCRF page and the actual dose description from IWRS study drug dispense dataset
- Total dose (in mg): this is calculated by the number of active injections taken during Period 2 multiplies by a dose of 80 mg

Duration of Exposure to Study Treatment during the Open-Label Treatment Period (Period 3)

The duration of exposure to ixekizumab Q4W only or ixekizumab Q4W step up to Q2W dosing in Period 3 will be calculated as:

Duration of exposure (days)

= *Date of last visit (scheduled or unscheduled) in Period 3]*

– *Date of first Q4W dosing in Period 3 + 1*

The number and percentage of patients in each of the following categories will be included in the summaries:

- >0, ≥7 days, ≥14 days, ≥30 days, ≥60 days, ≥90 days, ≥120 days, ≥180 days, and ≥280 days. Note that the same patients may be included in more than 1 category.
- >0 to <7 days, ≥7 to <14 days, ≥14 to <30 days, ≥30 to <60 days, ≥60 days to <90 days, ≥90 to <120 days, ≥120 to <180 days, ≥180 to <280 days, and ≥280 days.

Duration of Exposure to Ixekizumab Treatment during the Combined Treatment Period (Blinded Treatment Period (Period 2) and Open-Label Treatment Period (Period 3))

The duration of exposure to ixekizumab in Combined Period will be calculated, for patients who received at least one dose of ixekizumab, as:

Duration of exposure (days)

= Date of last visit (scheduled or unscheduled) in Combined Treatment Period]

– Date of first ixekizumab dose in Combined Treatment Period + 1

The number and percentage of patients in each of the following categories will be included in the summaries:

- >0, ≥7 days, ≥14 days, ≥30 days, ≥60 days, ≥90 days, ≥120 days, ≥180 days, ≥280 days, ≥365 days, and ≥548 days. Note that the same patients may be included in more than 1 category.
- >0 to <7 days, ≥7 to <14 days, ≥14 to <30 days, ≥30 to <60 days, ≥60 days to <90 days, ≥90 to <120 days, ≥120 to <180 days, ≥180 to <280 days, ≥280 to <365 days, ≥365 to <548 days, and ≥548 days.

